4.0 Inclusion and Exclusion Criteria

Study Population – A total of 70 men and women will be screened for inclusion in this study. 24 men and women with chronic insomnia will be enrolled to receive study therapy over a 3-month period. This study will focus on adult men and women (30- 60 years old) with a chronic complaint of insomnia and concomitant objective short sleep duration, based on both clinical and polysomnographic criteria. All subjects will meet the Research Diagnostic Criteria (RDC) for insomnia (Edinger et al, 2004) and will demonstrate < 6 hours of sleep, as assessed by polysomnography (Table 1). In addition, they should meet the criteria for duration for more than one year because this is the population that is associated with hypercortisolemia and medical morbidity as shown in our previous experimental and epidemiological studies.

Table 1. Research diagnostic criteria (RDC) for insomnia.

Insomnia disorder
A. The individual reports one or more of the following sleep related complaints: 
 1. difficulty initiating sleep, 2. difficulty maintaining sleep, 3. waking up too early, or 4. sleep that is chronically non-restorative or poor in quality.
B. The above sleep difficulty occurs despite adequate opportunity and circumstances for sleep.
C. At least one of the following forms of daytime impairment related to the nighttime sleep difficulty is reported by the individual: 
 1. fatigue/malaise; 2. attention, concentration, or memory impairment; 3. social/vocational dysfunction or poor school performance; 4. mood disturbance/irritability; 5. daytime sleepiness; 6. motivation/energy/initiative reduction; 7. proneness for errors/accidents at work or while driving; 8. tension headaches, and/or GI symptoms in response to sleep loss; and 9. concerns or worries about sleep.

Our participants will be middle-aged adults since objective sleep duration significantly correlates with age in an inverse manner. We will not exclude insomniacs with minor forms of anxiety or depression, i.e., dysthymic disorder, since these conditions are highly comorbid in chronic insomniacs (Buysse et al, 1993; Kales and Kales, 1984; Buysse et al, 1994a; Buysse et al 1994b). However, insomniacs with a current diagnosis of a major mental disorder, i.e., schizophrenia, major depression, will be excluded from the study because these conditions are associated with the primary outcome variables of this study. In addition, we will exclude subjects with morbid obesity (BMI > 39) because, at this level, obesity is frequently associated with frequent sleep pathology, i.e., apnea, EDS, and significant medical morbidity (Vgontzas et al, 1994; Vgontzas et al, 1998).

Participants with an apnea/hypopnea index (A/HI) > 5 or periodic limb movements > 5 per hour of sleep will be excluded from the study. Also, subjects with a primary disorder of EDS, e.g., narcolepsy, or subjects with a history of shift work or circadian disorder will be excluded from the study (Vgontzas and Kales, 1999; Roehrs et al, 2005; Boggild and Knutsson, 1999) (Table 2).

Table 2. Inclusion/exclusion criteria.

Inclusion	Exclusion
Chronic insomnia (RDC) with a duration \geq 1 year Objective short sleep duration (< 6h) BMI < 39 Age range: 30-60 Equal number of men and women	Major mental illness Substance abuse/dependence Sleep apnea (apnea/hypopnea index \geq 5) PLMD (periodic limb movements \geq 5) Objective normal sleep duration (\geq 6h) Primary disorders of EDS, i.e., narcolepsy Shift work or circadian disorders Diabetes, chronic renal failure, hepatic insufficiency, chronic heart failure Current use of hypnotics or sleep inducing sedative antidepressants

RDC = research diagnostic criteria; PLMD = periodic limb movements disorder

Subjects treated for diabetes or suffering from chronic renal failure or hepatic insufficiency or chronic heart failure will be excluded from the study. Also, because of the known effects of steroids on sleep, subjects on those medications will be excluded from the study. A family history of diabetes will be recorded during the medical history and physical examination and controlled within our analyses. Also, the potential effects of other medications or substances, such as alcohol or smoking, will be controlled within our analyses. Subjects with a diagnosis of substance abuse or dependence will be excluded from the study due to the potential effects of these substances on sleep and metabolism. Patients should be free of hypnotic use or sedative antidepressants administered at bedtime to improve sleep for one month before entering the study. Finally, patients using psychotropic medications, i.e., SSRI, who do not meet the criteria for a current major psychiatric disorder, and have continuous complaints of insomnia, will be included in the study. This is because a large portion of insomniacs consist of depressed individuals whose depression improved but still they have complaints of chronic insomnia. Potential confounding effects of medication on some of the outcome measures, i.e., objective sleep duration, will be dealt with in the analysis

Women and Minority Inclusion – In this project, we will include middle-aged men and women 30- 60 because they represent the majority of patients with insomnia in the general and clinic population. Women who are pregnant or breastfeeding will not be enrolled in the study. We plan to recruit about 21% of subjects belonging in minority groups. The racial and ethnic distribution shown in the Targeted/Planned Enrollment Table reflects the general demographics of our region. Minorities will be recruited from our clinics as well as through advertisements in papers with large groups of minority readers, such as Harrisburg, PA and Lebanon, PA.

IRB Protocol No. 35933
Version Date: 11/10/2015

Inclusion of Children – The prevalence and clinical characteristics of insomnia in children is not well established. In fact, current literature indicates that the etiology, clinical and sleep laboratory characteristics of insomnia in children are different than that in adults, i.e., bed-resistance, family dynamics, absence of sleep-related worry, etc. Most importantly, there is not sufficient evidence to use pharmacologic treatment in childhood insomnia.

5.0 Recruitment and Consent Process

[figure not shown]
When potential participants respond to an advertisement, a structured phone script or online script and interview is used to explain study procedures and determine eligibility. A member of the research team will then offer eligible participants the opportunity to participate in the study by scheduling a visit and sending a copy of the consent form for thorough review prior to the visit. At the time of the visit, the participant signs the consent form and is enrolled in the study. Potential participants may also be identified by clinicians in the Sleep Disorders Clinic and offered information about the study.

6.0 Study Procedures

Screening phase

The subjects' diagnoses of insomnia and other sleep disorders will be established by a clinical sleep history conducted by a clinical psychiatrist or psychologist who practices sleep medicine. The subjects that meet the research diagnostic criteria (RDC) for insomnia will be included in the study (see Table 1). The subjects' sleep patterns will be assessed via a sleep diary and actigraphy (for two weeks) prior to their visit to the sleep lab. Each subject will be monitored continuously for eight hours for one night in the sleep unit of the GCRC according to standard techniques (Rechtschaffen and Kales, 1986; Iber et al, 2007.). The first night will serve as a screening night for the presence of sleep apnea or periodic limb movements, and an adaptation night to control for "first night" effects. Prior to or during their visit to the sleep unit, the participants will be assessed for psychiatric disorders using a Structured Clinical Interview for DSM-IV, the Mini International Neuropsychiatric Interview (MINI ; Sheehan et al, 2006).

Figure 1. Screening phase, randomization of patients with insomnia.

Randomized Clinical Trial of Trazodone vs. CBT

a. Baseline measures – Following the screening night, the subjects that will enter the randomized trial will be monitored in the sleep laboratory continuously for 8 hours for 2 consecutive nights according to standard techniques (Rechtschaffen A, Kales A, 1968) (Table 3). Following the first night in the sleep laboratory, the participants will be admitted to GCRC for a complete semi-structured medical history and physical examination. Blood, urine and saliva will be collected and an electrocardiogram (EKG) will be performed. A pregnancy test will be performed on females of child bearing age. Following the second night in the sleep laboratory, daytime sleepiness and fatigue, nighttime sleep quality and quantity, and mood will be assessed subjectively with standardized self-reported questionnaires.

b. Randomization Scheme for Intervention – Subjects will be randomly assigned by our statistician into either a trazodone or a CBT program. Between the two intervention groups, we will attempt to have similar BMI, gender, and age distributions. If a patient is randomized and enters the randomization trial, then the patient will be considered enrolled in the study.

c. Completion of Study Visit – After 3 months on trazodone or CBT, the patients will undergo a repeat of the baseline evaluation as noted below (Table 3). This will include a complete physical examination, 2-night, 8-hour polysomnography, two-week

IRB Protocol No. 35933
Version Date: 11/10/2015

actigraphy & sleep diary, blood, urine, and saliva collection, and subjective measures of nighttime sleep and daytime functioning.

d. Once patients have completed 3 months of study, they will be followed-up again 6 months later. The same procedures performed during the baseline and post treatment phase will be repeated.

Table 3. Study design of randomized trial of trazodone vs. CBT

	Screening	Baseline	CBT Weekly Visits	Trazodone Monthly Visits	3 months	9 months
Structured Clinical Interview (MINI)	X					
Polysomnography & Video Recording						
1 night	X					
2 nights		X			X	X
Actigraphy						
2 weeks	X	X			X	X
Pregnancy Test	X	X				
Biomarkers						
Urinalysis		X			X	X
Urine Drug Screen		X			X	X
Blood Count		X			X	X
Blood Chemistries		X			X	X
Lipid Panel		X			X	X
Thyroid		X			X	X
Saliva cortisol		X			X	X
Blood Inflammation		X			X	X
Blood Insulin sensitivity		X			X	X
Medical history & physical exam.		X			X	X
EKG		X			X	X
Subjective Measures						
Post Sleep Assessment	X	X			X	X
Sleep diary	X	X	X	X	X	X
PSQI		X			X	X
ISI		X	X	X	X	X
PSAS		X			X	X
APS		X			X	X
FIRST		X			X	X
POMS-F		X			X	X
MFI		X			X	X
ESS		X			X	X
SSS	X	X			X	X
BDI-II		X			X	X
BAI		X			X	X
HAD-S		X			X	X
DBAS		X			X	X

d. Intervention Design – The CBT protocol used in this project will include evidence-based, behavioral and cognitive techniques; it will consist of what is called a “multimodal CBT treatment” covering sleep hygiene, stimulus control, sleep restriction, and cognitive therapy (Perlis et al, 2005).

A session-by-session schedule of the CBT treatment program is presented in Table 4. The 1st intervention session will present a conceptual cognitive-behavioral model of insomnia (Perlis et al, 2005) and the patient will receive sleep hygiene instructions. A brief presentation of the cognitive-behavioral model of insomnia proposed by Perlis et al (2005) will be explained to the patients and will serve as the basis to present all clinical procedures that will be used during treatment. The role of sleep-related behaviors and habits will be addressed, and a standard handout with sleep hygiene instructions will be given to the patient at the end of the session (Perlis et al, 2005). The 2nd session will introduce stimulus control and sleep restriction therapies, which have shown to be strongly efficacious in insomnia (Perlis et al, 2005). The goals of these therapies are: to reduce activities incompatible with sleep and develop positive associations of good sleep with the bedroom, increase sleep-wake specificity by avoiding napping in the day and getting up if wakeful at night, increase sleep efficiency by spending less time in bed and build up the natural sleep drive, and establish regular sleep habits and keep to a consistent pattern from night to night throughout the week. Because stimulus control and sleep restriction involves getting up from bed and going to other room, sessions 3rd and 4th will focus on addressing difficulties associated with these techniques. The 5th session will introduce the cognitive therapy component. Cognitive therapy is a psychotherapeutic method designed to change a person's beliefs, expectations, appraisals, and attributions (Morin, 1993; Perlis et al, 2005). In the context of insomnia, cognitive therapy seeks to change sleep expectations, catastrophic beliefs about the causes and consequences of insomnia, and beliefs about sleep-promoting practices. This intervention is predominantly verbal in nature and is more time consuming to implement in-session than behavioral procedures described in previous sessions. In fact, the 6th session will focus on cognitive restructuring, i.e., changing the patient's dysfunctional concerns and beliefs about sleep and insomnia. The 7th session will give end to the cognitive restructuring component but will also address difficulties associated with all clinical procedures described. The 8th session will integrate all clinical procedures as to improve long-term adherence, relapse prevention and will also include a post-treatment assessment, as presented in Table 3.

Table 4. A session-by-session schedule of the CBT program

Session	New/Review*	Content	Duration
1	N	Conceptual model and sleep hygiene	50 min
2	N	Setting up sleep restriction and stimulus control, Set prescription for sleep restriction	50 min
3	R	Sleep restriction and stimulus control treatment gains and compliance	50 min
4	R	Sleep restriction and stimulus control treatment gains and compliance	50 min
5	N	Cognitive therapy	50 min
6	R	Cognitive therapy	50 min
7	R	Cognitive therapy, sleep restriction, and stimulus control gains and compliance	50 min
8	N	Discuss relapse prevention Post-treatment assessment	50 min

* New/Review refers to the introduction of a new clinical component vs. a review of the outcomes and adherence of previously introduced components.

This **CBT protocol** is designed to be implemented over a period of 12 weeks, with consultation sessions held on a weekly basis (Perlis et al, 2005). There will be 2 sessions devoted to baseline evaluation, along with a 2-week baseline sleep diary and actigraphy monitoring period, followed by 8 therapy sessions. This number of sessions is needed to present a conceptual behavioral model of insomnia, describe all clinical procedures and their rationale, provide enough time for patients to experiment with those procedures at home, and to problem-solve difficulties encountered during home practice. Clinical sessions will be held weekly, to ensure continuity between sessions. The treatment program described here has been validated according to specific parameters (Perlis et al, 2005). Individual therapy sessions will last approximately for 50 minutes. Each therapy session is highly structured and covers a different aspect of treatment. Although their specific content varies on the technique presented/used, most sessions are structured according to the agenda outlined in Table 5.

Table 5. CBT session agenda

-
- Review sleep diary.
 - Evaluate compliance with clinical procedures and homework assignment.
 - Identify problems during home practice and strategies for promoting treatment adherence.
 - Introduce new treatment component and its rationale.
 - Present didactic material supporting this component.
 - Review homework assignments for the upcoming week.
-

The very first item of the agenda is to review the sleep diary for the previous week. This provides a clear message to the patient that self-monitoring is expected and is an essential component of therapy. The next step is to check the extent to which the patient has complied with previous recommendations. After problem solving adherence issues, a new treatment component is introduced. Each procedure is described along with its rationale and objectives. Handouts will always be provided to consolidate the new information presented during the session. The final item on the agenda is to review homework assignment for the upcoming week giving a written summary to the patient.

The **trazodone group** will receive a standard handout on sleep hygiene instructions and subsequent biweekly and monthly visits to check treatment effectiveness, adherence and possible side-effects, if they occur, and also follow-up review of sleep hygiene practices. All patients will receive a standard dose of trazodone 50 mg. in their first visit and will be followed-up with 2 additional biweekly visits. During these biweekly visits, doses will be adjusted according to drug effectiveness and possible side-effects. Consecutive visits will be scheduled monthly and will focus on assessing treatment effectiveness, adherence and possible side-effects and need to adjust medication doses.

Techniques

1. Medical History and Physical Examination

Each subject will have a complete medical history and physical examination using a semi-structured format and a battery of clinical tests, including complete blood count, liver function test, urinalysis, lipid panel, thyroid indexes, and electrocardiography. Pre-menopausal women will also have a pregnancy test performed. Blood pressure will be measured in the morning and in the evening using a pneumoelectric microprocessor-controlled instrument. The recorded blood pressure will be the average of 3 consecutive readings during a 5-minute period following 10 minutes of rest in the supine position. Anthropometric measures will include height, weight, neck size, and waist and hip measurements according to standard procedures. Specifically, neck size is measured at the superior border of the cricothyroid membrane with the subject in the upright position. Waist is measured at or 1 cm above the umbilical midline and hip at the widest area around the buttocks.

2. Objective assessment of Nighttime Sleep

a. Polysomnography – Each subject will be monitored continuously for eight hours for 2 consecutive nights (adaptation night and one baseline night) according to standard techniques (Rechtschaffen A, Kales A, 1968). Also, to improve the accuracy and reliability of our nighttime sleep measures, the subjects' typical sleep time at home will be assessed objectively via actigraphy for two weeks before the sleep laboratory recordings (see below) and during the sleep lab recordings. Respiration will be monitored throughout the night by thermocouples at the nose and mouth (Salter Labs) and nasal cannula/pressure and by thoracic strain gauges. We will use both thermocouples and nasal cannula because it has been reported that the pressure signal identifies transient elevated upper airway resistance not detected conventionally (Iber et al, 2007). An apnea/hypopnea index ≥ 5 will be used to define the presence of sleep apnea.

b. Actigraphy – An actigraphy monitor (ActiGraph GT3X) will be placed on the wrist of the nondominant hand of subjects. The subjects will be asked to keep an actigraphy log for two week periods in which they note daily time to bed, time out of bed, or times when the device is removed (e.g., taking a bath, swimming).

3. Subjective assessment of Nighttime Sleep and Arousal

a. Post-sleep Assessment – Throughout the study, subjects will complete a post-sleep questionnaire upon awakening each morning in the sleep lab and will estimate time to fall asleep, number of nightly awakenings, total sleep time, soundness and quality of sleep, and morning sleepiness.

b. Sleep Diary – A 2-week sleep log or diary will be used for assessment of the subjects' perceived sleep patterns at the screening phase, at the onset of the study, during the intervention period, at the end of the intervention and at follow-up.

c. Sleep Quality – The Pittsburg Sleep Quality Index (PSQI) will be used for assessment of the subjects' overall sleep quality at the onset of the study, at the end of the intervention and at follow-up (Buysse et al, 1989).

d. Insomnia Severity – The Insomnia Severity Index (ISI) will be used for assessment of the subjects' overall perceived insomnia severity at the onset of the study, during the intervention period, at the end of the intervention and at follow-up (Bastien et al, 2001).

e. Pre-sleep Arousal – The Pre-Sleep Arousal Scale (PSAS) will be used for assessment of the subjects' perceived pre-sleep cognitive and somatic arousal at the onset of the study, at the end of the intervention and at follow-up (Nicassio et al, 1985).

f. Arousability – The Arousability Predisposition Scale (APS) will be used for assessment of the subjects' perceived overall tendency to present high levels of cognitive and emotional arousal at the onset of the study, at the end of the intervention and at follow-up (Coren, 1988).

g. Stress-related Insomnia – The Ford Insomnia Response to Stress Test (FIRST) will be used for assessment of the subjects' overall perceived likelihood of having sleep disturbances in association with specific and common stressful events at the onset of the study, at the end of the intervention and at follow-up (Drake et al, 2004).

4. Assessment of Daytime Functioning

a. Sleepiness and Fatigue – Subjects will estimate degree of sleepiness/alertness after awakening in the sleep lab with a 10-cm analog scale that ranges from "extremely sleepy" to "not sleepy" and the Stanford Sleepiness Scale (SSS) (MacLean et al, 1992). The Epworth Sleepiness Scale (ESS) will be used for assessment of the subjects' overall sleepiness at the onset of the study, at the end of the intervention and at follow-up (Johns, 1991). The Fatigue subscale of the Profile of Mood States (POMS-F) (McNair et al, 1971.), and the Multidimensional Fatigue Inventory (MFI) (Smets et al, 1995) will be used for assessments of the subjects' overall fatigue at the onset of the study, at the end of the intervention and at follow-up.

b. Mood – The Beck Depression Inventory-II (BDI-II) will be used for assessment of the subjects' overall severity of depressive symptoms at the onset of the study and at the end of the intervention (Beck et al, 1996). The Beck Anxiety Inventory (BAI) will be used for assessment of the subjects' overall severity of anxious symptoms (somatic component) at the onset of the study, at the end of the intervention and at follow-up (Osman et al 1997). The Anxiety subscale of the Hospital Anxiety and Depression Scale (HAD-S) will be used for assessment of the subjects' overall severity of anxious symptoms (cognitive component) at the onset of the study, at the end of the intervention and at follow-up (Zigmond and Snaith, 1983).

c. Cognition – The Dysfunctional Beliefs and Attitudes about Sleep scale (DBAS) will be used for assessment of the subjects' sleep cognitions (i.e., causal attributions of insomnia, perceived consequences of insomnia, sleep requirements expectations, control and predictability of sleep, and beliefs about sleep-promoting practices) at the onset of the study, at the end of the intervention and at follow-up (Espie et al 2000).

5. Assessment of the Stress System, Inflammation, and Insulin Resistance

a. Stress System – We propose to sample saliva at five time points during the day, i.e. 8:00 before breakfast, 12:00 before lunch, 3:00 pm, 6:00 pm, and 9:00 pm. It has been demonstrated that five samples are adequate to examine circadian variation of cortisol secretion (Pervanidou et al, 2007a; Pervanidou et al, 2007b). No food or exercise would be allowed at least half an hour before sample collection. Each sample will be collected by having the participant place a cotton swab in his or her mouth for 2 minutes or chew it for 1 minute. These samples will be collected on Day 2 of the baseline and follow-up phases (3 and 9 months) of the study. The cotton swab will then be placed inside a plastic tube and kept in the refrigerator at 0-4°C. Salivary cortisol will be extracted from the cotton by centrifuging the plastic tubes and cotton at 100g for 8 minutes to separate the saliva into the outer tube. The cotton will be removed and all samples will be stored at -85°C.

b. Inflammation Markers– TNF α , TNFr1 and IL-6 will be measured in two single serum samples on Day 2 (evening and morning pre- and post-sleep recording) because their concentration varies during the 24-hour sleep-wake cycle. Blood will be collected during the baseline and follow-up phases (3 and 9 months) of the study. Serum TNF α , TNFr1, and IL-6 will be measured by ELISA (R&D Systems, Minneapolis, MN) (Vgontzas et al, 2004; Vgontzas et al, 2007; Vgontzas et al, 1997; Vgontzas et al, 2004; Vgontzas et al, 2008).

c. Insulin Sensitivity – Whole-body insulin sensitivity can be measured with the euglycemic insulin clamp technique, which measures insulin resistance (IR) directly and is considered the “gold standard”. However, the intensity, complexity and risks of the method make it unsuitable for large studies such as ours. The use of a fasting glucose to insulin (G/I) ratio is the simplest and easiest way technically and appears to provide a reasonable estimate of tissue sensitivity to insulin in large samples. Many studies have shown that simple indices of insulin sensitivity derived from fasting glucose and insulin levels, such as homeostasis model assessment (HOMA) (Ip et al, 2002; Punjabi et al, 2002) and Quantitative Insulin Sensitivity Check Index (QUICKI), are simple, accurate methods for assessing insulin sensitivity in large studies (Quon, 2001; Katz et al, 2000). The reliability of the G/I ratio is expected to be very good in our study given that overnight fasting is well-controlled within the sleep lab environment. Blood samples will be collected on day 2 (evening and morning pre-and post-sleep recording) during the baseline and follow-up phases (3 and 9 months) of the study.

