Given the well-established association of hypercortisolemia with significant medical morbidity, i.e., hypertension, diabetes, metabolic syndrome, osteoporosis, and others (80), we examined the joint effects of insomnia and short sleep duration on the risk of medical morbidity, i.e., hypertension, diabetes, and neurocognitive deficits, and mortality in a general population sample of 1,741 men and women randomly selected from Central Pennsylvania (Penn State Cohort) (Bixler et al, 1998; Bixler et al, 2001). In the first study, the highest risk of hypertension was in insomniacs with < 5 hour sleep duration group (OR = 5.0), and the second highest in insomniacs who slept 5-6 hours (OR = 3.5) when compared to the normal sleeping and ≥ 6 hour sleep duration group (Vgontzas et al, 2009a). In the second study, we examined the joint association of insomnia and objective short sleep duration on the risk for diabetes. A significantly increased risk for diabetes was observed in the group of the most severe insomniacs, i.e., insomnia with objective sleep duration < 5 hours (Vgontzas et al, 2009b). In the third study, significant neurocognitive deficits were observed only in insomniacs with < 6 hours as compared to controls or insomniacs with ≥ 6 hours (Fernandez-Mendoza et al, 2010). In our fourth study, we reported that objective short sleep duration (< 6 hours) in male insomniacs predicts mortality over a period of 14 years of follow-up (Vgontzas et al, 2010). Finally, in the same cohort, we examined the differential psychological profile of insomniacs with objective short and normal sleep duration (Fernandez-Mendoza et al, 2011). This latter study revealed that insomniacs with normal sleep duration present with

sleep misperception (i.e., the tendency to underestimate sleep duration) and anxious-ruminative and poor coping resources personality traits.

Based on these studies, we have recently suggested that objective sleep duration in chronic insomnia is a marker of the biological severity of the disorder.

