3.0 Study Design and Methods

1. Rationale – Current treatments for chronic insomnia are either partially effective and/or associated with poor outcomes in objective measures of nighttime sleep. Specifically, CBT, the most widely used therapeutic modality, is not associated with a satisfactory and clinically significant increase in objective sleep duration (Okajima et al, 2010). Furthermore, it is not known whether CBT can reverse the activation of the stress system, i.e., hypercortisolemia, associated with insomnia with objective short sleep duration. Sedative antidepressants, such as trazodone, have been shown in several studies to increase objective sleep duration and/or decrease cortisol levels (McCall, 2010). The goal of this interventional study is to assess the effect of trazodone vs. CBT in patients with chronic insomnia with objective short sleep duration.

All subjects will be randomly assigned into either a trazodone or a CBT group. The group assignment will be decided by our statistician so that the investigators

involved with subject recruitment and screening remain blind to the randomization process.

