11.0 Statistical Analysis of the Study

Analysis

a. Sample Size Calculation – This is a pilot study to collect preliminary data using two interventions, i.e., trazodone or CBT, with unknown effects for chronic insomnia with objective short sleep duration. Based on our previous experience with interventional studies, we suggest that 10 subjects per group will be adequate to detect a difference of 20 minutes in objective sleep duration between the two treatment interventions. To allow for an anticipated 20% attrition rate, 24 subjects will be assigned to a study intervention to ensure complete data from 20 participants. The results of this study will allow the establishment of sample size for any future studies. Our statistical consultant in this study is [name].

b. Analytic Plan

Specific Aim 1: Examine the Effect of Trazodone vs. CBT for the Primary Outcome Variables (objective and subjective sleep duration) in Patients with Chronic Insomnia with Objective Short sleep Duration

Throughout the analysis, we will compare the differences (end of the interventional study baseline) between the two groups of the outcome of interest (e.g., total sleep time).

Total Sleep Time, Polysomnography: Both at baseline and the end of the intervention, polysomnography will be measured for 2 consecutive nights. We will calculate the time-specific difference from the baseline to the end of intervention. Then, we will compare the two treatment conditions with respect to the overall mean change across all time points (“difference of difference”) using the two-sample t-test. Alternatively, repeated measures analysis of variance (ANOVA) will be used to compare treatment conditions with respect to polysomnographic total sleep time changes from baseline. The time and treatment condition main effects as well as interaction between time and treatment condition will be tested. Adjustments for multiple comparisons across different time points and between intervention groups will be performed. Potential confounders and interaction between treatment condition and confounder will also be examined. In the event that the distribution of polysomnographic total sleep time are not consistent with the assumptions of normality required for ANOVA, attempts will be made to find suitable transformation.

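### The allocation names no balancing method and leaves out baseline PSG sleep time, and the planned change-score test only partly makes up for it; adjust for that baseline and balance on it.

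*Combined protocol and SAP*

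**What the plan says.** Three parts of the combined protocol and SAP bear on this.

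- **Allocation.** Section 6.0, item b: "Subjects will be randomly assigned by our statistician into either a trazodone or a CBT program". The next sentence reads: "Between the two intervention groups, we will attempt to have similar BMI, gender, and age distributions". Section 3.0 states: "The group assignment will be decided by our statistician", and gives as the reason that staff who recruit and screen should stay blind to the process. Stratification, blocking, minimisation and sequence generation are not described anywhere.
- **Baseline sleep time.** It is not among the three balancing variables. Yet Section 1.0 says that "we have recently suggested that objective sleep duration in chronic insomnia is a marker of the biological severity of the disorder", and reports different hypertension odds ratios for insomnia with under 5 h of sleep (5.0) and with 5 to 6 h (3.5). Objective sleep duration is also a primary outcome (Section 2.0).
- **Size and analysis.** Section 11.0 says that "10 subjects per group will be adequate" for a 20-minute difference, and that "24 subjects will be assigned to a study intervention to ensure complete data from 20 participants". The primary outcomes are compared as change from baseline, by a two-sample t-test or alternatively by repeated measures ANOVA. Unspecified confounders are to be examined; baseline sleep time is not named as one.

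**The concern.** At 24 patients, plain randomisation cannot be relied on to give similar arms, and the text does not say what else will be done. The omitted variable is the one most likely to matter, because baseline sleep time predicts its own change: patients who start shorter tend to gain more. If one arm happens to start shorter, part of its apparent advantage is regression to the mean. The target contrast is only 20 min and about 10 patients per arm are expected to finish, so such a component could be a sizeable share of the observed difference. The result is also meant to set the sample size of later studies, so it would be carried forward.

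**Working it through.** **1. The plan's own figure.** Section 11.0 gives no SD, alpha, sidedness or power, so 10 per group cannot be reproduced. Solving backwards at two-sided alpha 0.05 and 80% power:

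SD of change = 20 / (√(2/10) × (1.960 + 0.842)) = 20 / 1.253 = 16.0 min (15.1 min with the t distribution).

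On attrition, 20 / (1 − 0.2) = 25, while 24 = 20 × 1.2. The gap is immaterial here.

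**2. Inputs for the imbalance.** From Section 11.0: 24 assigned in two groups, taken as 12 and 12; 20 completers; a target of 20 min. Assumed, because the documents give nothing: a between-patient SD of baseline sleep time of 30 to 60 min. As a rough guide, entry requires under 360 min, and a uniform spread over 240 to 360 min has SD 120/√12 = 35, over 180 to 360 min 180/√12 = 52. Also assumed: baseline-to-follow-up correlation r of 0.3 to 0.7 and equal variances, so that the slope b equals r.

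**3. Chance imbalance in baseline means.** SE = SD × √(2/n), and P = 2 × (1 − Φ(20/SE)).

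| Assumed SD (min) | SE, 12 per arm | P(difference above 20 min) | SE, 10 per arm | P(difference above 20 min) |
|---|---|---|---|---|
| 30 | 12.2 | 0.10 | 13.4 | 0.14 |
| 45 | 18.4 | 0.28 | 20.1 | 0.32 |
| 60 | 24.5 | 0.41 | 26.8 | 0.46 |

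With 12 per arm the probability passes one half only if the SD exceeds about 73 min. If the 16.0 min from step 1 were right, the matching baseline SD would be 16.0/√(2(1 − r)) = 13.5, 16.0 or 20.7 min at r = 0.3, 0.5 or 0.7, and the probability would stay below 2%.

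**4. What the change score leaves behind.** Shift in the contrast = imbalance × (1 − b). For 20 min: 20 × 0.7 = 14 min at b = 0.3; 20 × 0.5 = 10 min at b = 0.5; 20 × 0.3 = 6 min at b = 0.7. For a one-SE imbalance at SD 45 and b = 0.5: 18.4 × 0.5 = 9.2 min.

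**5. What adjustment gains.**

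- SE of the change-score contrast = SD × √(2(1 − r)) × √(2/n).
- SE of the ANCOVA contrast = SD × √(1 − r²) × √(2/n).
- Ratio = √((1 + r)/2) = 0.806, 0.866, 0.922 at r = 0.3, 0.5, 0.7: reductions of 19%, 13% and 8%.
- Example, SD 45, r 0.5, 12 per arm: 45 × 1 × 0.408 = 18.4 min, against 45 × 0.866 × 0.408 = 15.9 min.

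This ignores the small cost of estimating the slope.

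**6. What balancing gains.** Simulation of 20,000 trials of 24 patients, chance of an imbalance of 20 min or more:

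| Assumed SD (min) | Plain 12:12 | Two sleep strata, blocks of 4 | Minimisation (0.8 to the favoured arm) |
|---|---|---|---|
| 30 | 10% | 1% | 0.2% |
| 50 | 33% | 13% | 3% |
| 60 | 42% | 20% | 6% |

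The simulation balances on sleep time alone, using the same value in which imbalance is measured. Balancing on a screening-night value, with other factors, would do less well.

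**The case against.** The strongest reply is that chance imbalance under random allocation is ordinary sampling error. It does not bias the estimate, and the t-test's standard error already includes it. That stands: the gain is in precision and in how well the single realised comparison can be trusted. ANCOVA alone also supplies most of it.

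Other points have partial force. Section 4.0 says that sleep duration falls with age, so balancing on age helps a little. The examination of confounders in Section 11.0 could come to include baseline sleep, but nothing commits it to. The order of baseline nights and allocation is not fully explicit: Section 6.0 describes the two baseline nights before the randomisation step, but does not say that they are scored by then. However, a PSG must be read beforehand, since sleep apnoea, limb movements and the 6-hour limit decide entry.

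A reader might infer more than the text supports:

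- **That assignments will be adjusted by judgement.** Section 6.0 says that they are random, and the stated attempt is compatible with stratification or minimisation. The method is unnamed; it is not shown to be discretionary.
- **That concealment is weak.** Section 3.0 gives the task to the statistician precisely so that recruiters stay blind.
- **That men and women will probably split unevenly.** Probabilities under plain 12:12 allocation do not describe a plan that intends to balance gender.

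**Conclusion.** The point holds as a gap worth closing. The allocation method is unnamed, baseline PSG sleep time is neither balanced nor adjusted for, and the change-score analysis corrects only part of an imbalance.

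It would be too strong to call a 20-minute imbalance likely: at assumed SDs of 30 to 60 min the chance stays below even odds. It is negligible if the spread is as small as step 1 would require under the assumed equal variances. It would also be wrong to compare a 20-minute baseline difference directly with the 20-minute target, since only the regression-to-the-mean part reaches the contrast. The gain from adjustment rests on the assumed correlation and equal variances.

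**What to change.** 1. **Analysis (Section 11.0).** Replace the unadjusted change-score t-test for PSG sleep time by an ANCOVA with continuous baseline PSG sleep time and the allocation factors as prespecified covariates. Name the baseline recording used.
2. **Allocation (Section 6.0, item b).** Replace the stated attempt at similarity with a computer-run minimisation with a random element, on sex and PSG sleep time, adding age or BMI if wanted. Use the screening-night recording, which already has to be read for eligibility, so assignment need not wait for the baseline nights. The protocol's own division at 5 h would serve if categories are preferred.

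The cost is one paragraph in each section, a short script for the statistician who already makes the assignments, and one degree of freedom per covariate. With about 20 completers, that is a reason to keep the list of factors short. If only one change is made, the first brings most of the benefit; the second also settles how patients are allocated.
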